5.9 Statistics and Data Analysis for Prevention for Positives

5.9.1 Endpoints

The primary endpoint for the effectiveness of the Prevention for Positives component of the study is the following:

• The proportion of participants reporting any unprotected vaginal or anal sex the last time they had sex, evaluated for all partners and also separately for primary and non-primary partners.

The secondary endpoints for the effectiveness of CARE+ Positive Prevention component of the study are the following:

- Proportion of those who had unprotected vaginal or anal sex the last time they had sex with negative or unknown HIV status partners, evaluated for all partners and also separately for primary and non-primary partners.
- The frequency of participants reporting any unprotected vaginal or anal sex in the previous three months with non-primary partners.
- The number of different persons with whom the participant shared needles or works (including cookers and cottons) in the previous three months.

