5.3.1 Inclusion Criteria

The inclusion criteria for this study component are as follows:

- All individuals who are permitted to consent for HIV care according to New York State or Washington, D.C. law
- Receiving care at the selected HIV care sites in the Bronx or Washington, D.C.
- Have attended the clinic one or more times in the last seven months

- Able to understand either spoken English or Spanish
- Able and willing to provide informed consent

Subjects enrolled into the Prevention for Positives component of the study will participate in the patient survey (see Section 6.0).

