5.9.2 Accrual, Follow-up, and Sample Size

The primary behavioral endpoint of this study component is the proportion of patients reporting any unprotected vaginal or anal sex the last time they had sex. In the Strategies for Management of Antiretroviral Therapy (SMART) study, at 11.2% of visits participants reported any unprotected anal or vaginal sex in the previous two months. Using post-enrollment data; 5.4% of patient visits included a report of unprotected anal or vaginal sex with an HIV-uninfected partner in the previous two months.

Individual randomization will occur, potentially stratified by gender.

Using a 2-sided alpha of 5%, and calculating the sample size required to achieve 90% power to detect differences in percentages of participant visits where high-risk behaviors are reported in each arm, Table 4 presents a number of assumptions. A within-person, ICC of 0.3-0.4 is assumed, based on data from the SMART trial behavioral endpoints.

Assuming at least one follow-up visit for 90% of enrollees, and an average number of visits per participant of 3.75 amongst retained participants, the study will enroll 660 per arm (1320 in total) to allow for loss due to attrition and loss to follow-up. It is estimated that around 110 participants will be recruited per HIV care site, with a target enrollment of two subjects/day per site. Target enrollment should be reached within eight-12 months of initiation, and accrual will be terminated at 1320 participants or after approximately 12 months of accrual, whichever occurs first.

It is anticipated that a total of approximately 1320 individuals will be randomized. Data will be collected from each person an average of 4 times during the study (out of four possible visits following enrollment at month 0, *i.e.* months 3, 6, 9, and 12). Allowing for

loss to follow-up, with 522 people available for assessment per arm, the study has 90% power to detect a decrease from 11% to 8% in proportion of patients reporting any unprotected vaginal or anal sex at a given visit during the study.

Control (%)	Intervention (%)	Mean Number of Visits	Intra-class Correlation	Number of People per Arm	Intra-class Correlation	Number of People per Arm
5.4%	3.0%	4	0.4	378	0.3	373
5.4%	3.5%	4	0.4	638	0.3	630
5.4%	4.0%	4	0.4	1240	0.3	1223
7.5%	4.0%	4	0.4	243	0.3	238
7.5%	4.5%	4	0.4	344	0.3	337
7.5%	5.0%	4	0.4	515	0.3	505
11%	7.5%	4	0.4	385	0.3	374
11%	8.0%	4	0.4	537	0.3	522
11%	8.5%	4	0.4	792	0.3	769

 Table 4:

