5.9.4 Data Analysis

Data to be analyzed for this study component will be obtained from the CARE+ electronic storage system and abstracted from participant's medical records. As participants proceed through the CARE+ intervention, their answers will automatically be stored electronically in a secure system. Access to the storage system will be limited to essential personnel. CD4 cell counts and HIV RNA levels obtained from month 0 through month 12, will be extracted from participant's medical records to enable individual-level subgroup analyses of adherence and virologic responses among CARE+ participants who are receiving versus not receiving FIs for virologic suppression, as well as other subgroup analyses.

The primary behavioral endpoint of this study component is the proportion reporting any unprotected vaginal or anal sex the last time they had sex.

Effectiveness of the CARE+ Prevention for Positives component will assess differences in proportion reporting self-reported risk behavior for participants in the CARE+ Prevention arm compared to the control arm. GEE methods for repeated measures will be used to assess the difference in proportion reporting high-risk behavior between the two study arms for participants. Major subgroup analyses for those on ART and not on ART will be conducted.

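### The CARE+ primary endpoint has no look-back limit, so it can record acts from before randomisation, and the stated 90% power belongs to a different, two-month outcome

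*Protocol*

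**What the plan says.** Protocol 5.9.1 defines the primary endpoint as "The proportion of participants reporting any unprotected vaginal or anal sex the last time they had sex". Section 5.9.2 repeats this, and section 5.9.4 does so again: "The primary behavioral endpoint of this study component is the proportion reporting any unprotected vaginal or anal sex the last time they had sex". None of the three places sets a look-back period or says how to count someone with no recent sex.

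Two of the three secondary endpoints in 5.9.1 do carry a period, for example "The frequency of participants reporting any unprotected vaginal or anal sex in the previous three months with non-primary partners". The other, on partners of negative or unknown status, is also a last-sex measure without one.

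The only recency criterion for entry concerns clinic visits: "Have attended the clinic one or more times in the last seven months" (5.3.1). The exclusion criteria in 5.3.2 do not mention sexual activity. Section 5.7 places the computer sessions at months 0, 3, 6, 9 and 12.

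For the sample size, 5.9.2 takes its rate from an earlier study in which "at 11.2% of visits participants reported any unprotected anal or vaginal sex in the previous two months". It then states that "with 522 people available for assessment per arm, the study has 90% power to detect a decrease from 11% to 8" percent. The outcome named in that sentence is any unprotected act at a given visit, not the most recent act.

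**The concern.** There are two linked problems.

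1. **The endpoint can look back past randomisation.** Someone with no sex after enrolment has only an older act to report, and the intervention cannot alter it. Someone who has an unprotected act and then stops having sex continues to count as high-risk, although stopping may be a response to counselling. The first adds answers that carry no information about CARE+. The second hides a possible benefit.

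2. **The power statement is for another variable.** The planning rate is a windowed measure of any act, in which a person without recent sex is necessarily a no. The declared primary is an unwindowed measure of one act.

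At stake is whether a null result could be read as absence of effect, and whether 1320 participants is the right number for the outcome that decides the component.

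**Working it through.** **Step 1: reproduce the stated figure.** Inputs from 5.9.2 and Table 4: p1 = 0.11, p2 = 0.08, m = 4 visits, two-sided alpha 5%, power 90%, tabulated correlation 0.3 or 0.4. The cluster formula that reproduces Table 4 is

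n = 1 + (z0.975 + z0.90)² × [p1(1−p1)/m + p2(1−p2)/m + k²(p1² + p2²)] / (p1−p2)²

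- (1.960 + 1.282)² = 10.507.
- k = 0.3: bracket = 0.0979/4 + 0.0736/4 + 0.09 × 0.0185 = 0.04454. n = 1 + 10.507 × 0.04454/0.0009 = 521.0 (stated: 522).
- k = 0.4: bracket = 0.045835, n = 536.1 (stated: 537).
- Power at 522 = Φ(√(521 × 0.0009/0.04454) − 1.960) = Φ(1.285) = 90%.

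So 11% versus 8% is what drives the sample size. The match requires the tabulated 0.3 and 0.4 to be entered as a between-person coefficient of variation k, although the text calls them an intra-class correlation. That is a separate matter and is not counted here. The figures below keep the protocol's own formula.

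**Step 2: set the two outcomes side by side.**

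| | Declared primary | Planning rate |
|---|---|---|
| Acts counted | the most recent one | any |
| Look-back | none | two months |
| Person with no sex for two months | answer taken from an older act | no |
| Rate in the protocol | none | 11.2% of visits |

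The last-sex rate could be lower than 11%, because only one act counts. It could be higher, because there is no time limit, or because only people with a sexual occasion to report may enter the denominator. The protocol does not settle which.

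**Step 3: which visits can carry an act from before randomisation.** At month 3 this is anyone with no sex since enrolment. At months 6, 9 and 12 it is only those who still have had none. An act older than the previous visit is not enough, since it may still fall after randomisation.

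**Step 4: power at 522 per arm over assumed last-sex control rates.** Same formula, m = 4, k = 0.3. The control rates are assumptions. The second column keeps the 3-point difference. The third keeps the relative reduction 8/11.

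| Control rate | Power, 3-point difference | Power, same relative reduction |
|---|---|---|
| 5% | 99.9% | 58% |
| 8% | 97% | 78% |
| 11% | 90% | 90% |
| 15% | 79% | 97% |
| 20% | 67% | 99% |
| 30% | 52% | >99% |
| 40% | 44% | >99% |

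The two columns move in opposite directions, so even the sign of the error depends on facts that the protocol does not give.

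**The case against.** **Randomisation balances old acts.** This stands. Acts from before enrolment should be equally common in both arms in expectation, so the endpoint is not confounded. What remains is a loss of sensitivity.

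**Question wording or skip rules may sit in the interview or the procedures manual.** That is possible, and neither is shown. But the protocol defines the primary endpoint three times without a window, and its power sentence names another outcome. Interview logic would not repair the second point.

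**A last-act question is easier to answer than one about months of behaviour.** This is a fair reason to ask about the last act, and it is compatible with requiring that the act fall within a window.

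**A stronger reading is tempting: shrink the 3-point effect by the share of visits without recent sex.** The document does not support it.

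- The planning outcome already scores those visits as no in both arms, so 11% and 8% are averages over them.
- Let a be the share of such visits and s the unprotected share among the old acts reported there, equal in both arms. The rates become 11% + a·s and 8% + a·s, and the difference is still 3 points. Scaling it by 1 − a counts abstinence twice.
- The cost in this picture is a higher base rate. For example, with a = 20% and s = 11%/0.8 = 13.75% (both assumed), the control rate is 11% + 0.2 × 13.75% = 13.75%. That lies between the 11% and 15% rows, so power is between 79% and 90%.
- The share without sex since the last visit also overstates the share without sex since randomisation.

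The difference itself would shrink to the extent that CARE+ works by leading people to stop having sex. The protocol gives nothing from which to size that.

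**Conclusion.** The point holds in two parts. First, the unwindowed endpoint can record acts that the intervention could not affect, and it keeps counting people as high-risk after they stop having sex. Sensitivity is reduced by an amount that the document does not allow one to quantify. Second, the 90% power is arithmetically reproducible but is not established for the declared primary. At 522 per arm, over assumed control rates of 5% to 40%, it ranges from 44% to 99.9% with a fixed 3-point difference and from 58% to over 99% with a fixed relative reduction.

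A reader might infer that answers are out of date at every follow-up visit, or that the trial is underpowered by a known margin. Neither follows. The first is true only of participants with no sex after enrolment, and the direction of the second is unknown. The endpoint and its power basis should be reconciled before the component starts.

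**What to change.** At each follow-up visit, define the primary endpoint as an unprotected vaginal or anal act within a fixed window no longer than the three-month visit interval. It can be either the last act, if it fell in the window, or any act in the window. Count no sex in the window as a no, so that everyone assessed stays in the denominator.

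Then make the power statement refer to that same outcome:

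- Any unprotected act in the previous two months would match the planning rate directly.
- A three-month window, or a last-act version, has no rate in the protocol. State the assumed control rate and give power over a range, as in the table above.

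The cost is one date or window item in the existing computer interview, revised wording in 5.9.1, 5.9.2 and 5.9.4, and a recalculated power paragraph. The downside is one more recall item and possibly a different event rate, which could change the sample size needed.

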5.9.2 Accrual, Follow-up, and Sample Size

The primary behavioral endpoint of this study component is the proportion of patients reporting any unprotected vaginal or anal sex the last time they had sex. In the Strategies for Management of Antiretroviral Therapy (SMART) study, at 11.2% of visits participants reported any unprotected anal or vaginal sex in the previous two months. Using post-enrollment data; 5.4% of patient visits included a report of unprotected anal or vaginal sex with an HIV-uninfected partner in the previous two months.

Individual randomization will occur, potentially stratified by gender.

Using a 2-sided alpha of 5%, and calculating the sample size required to achieve 90% power to detect differences in percentages of participant visits where high-risk behaviors are reported in each arm, Table 4 presents a number of assumptions. A within-person, ICC of 0.3-0.4 is assumed, based on data from the SMART trial behavioral endpoints.

Assuming at least one follow-up visit for 90% of enrollees, and an average number of visits per participant of 3.75 amongst retained participants, the study will enroll 660 per arm (1320 in total) to allow for loss due to attrition and loss to follow-up. It is estimated that around 110 participants will be recruited per HIV care site, with a target enrollment of two subjects/day per site. Target enrollment should be reached within eight-12 months of initiation, and accrual will be terminated at 1320 participants or after approximately 12 months of accrual, whichever occurs first.

It is anticipated that a total of approximately 1320 individuals will be randomized. Data will be collected from each person an average of 4 times during the study (out of four possible visits following enrollment at month 0, *i.e.* months 3, 6, 9, and 12). Allowing for

loss to follow-up, with 522 people available for assessment per arm, the study has 90% power to detect a decrease from 11% to 8% in proportion of patients reporting any unprotected vaginal or anal sex at a given visit during the study.

Control (%)	Intervention (%)	Mean Number of Visits	Intra-class Correlation	Number of People per Arm	Intra-class Correlation	Number of People per Arm
5.4%	3.0%	4	0.4	378	0.3	373
5.4%	3.5%	4	0.4	638	0.3	630
5.4%	4.0%	4	0.4	1240	0.3	1223
7.5%	4.0%	4	0.4	243	0.3	238
7.5%	4.5%	4	0.4	344	0.3	337
7.5%	5.0%	4	0.4	515	0.3	505
11%	7.5%	4	0.4	385	0.3	374
11%	8.0%	4	0.4	537	0.3	522
11%	8.5%	4	0.4	792	0.3	769

 Table 4:
 Per-Arm Sample Size Required for 90% Power to Detect Difference in Proportion Reporting High Risk Behavior at a Visit, with Two-sided Alpha of 5%, Assuming Four Visits per Participant

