6.5 Study Procedures for the Survey of Patients

Once consented and enrolled in the Prevention for Positives component, the clinic study staff will train participants how to use the computer tablet. Randomization to intervention (SOC plus full CARE+/ACASI counseling session) or control arm (SOC alone) is done automatically within the software application following the user's login with an anonymous study ID. Up to 110 individuals will be assigned to each arm, per site. At the end of the first (baseline, month 0) session, both arms will be presented, via the computer tool, with a series of questions (the patient survey). This patient survey module will be repeated only one more time, at the end of the intervention (month 12).

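### Table 4 of Section 5.9.2 does not reflect the within-person ICC of 0.3-0.4 that it states; if that ICC is right, power for 11% vs 8% is about 66-72% in the planned design, not 90%

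*Protocol*

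**What the plan says.** Protocol Section 5.9.2 sizes the individually randomised CARE+ comparison on repeated visits per person. It sets the error rates ("Using a 2-sided alpha of 5%, and calculating the sample size required to achieve 90% power") and gives the correlation assumption as "A within-person, ICC of 0.3-0.4 is assumed, based on data from the SMART trial behavioral endpoints". Table 4 carries that assumption in two columns headed intra-class correlation, 0.4 and 0.3, with a mean of four visits. Its caption reads "Per-Arm Sample Size Required for 90% Power to Detect Difference in Proportion Reporting High Risk Behavior at a Visit". For 11% vs 8% the entries are 537 and 522.

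The text takes up the second entry: "with 522 people available for assessment per arm", it says, "the study has 90% power to detect a decrease from 11% to 8% in proportion of patients reporting any unprotected vaginal or anal sex".

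Enrolment is 660 per arm, 1,320 in all. Ninety per cent are expected to have at least one follow-up visit, and retained participants to average 3.75 visits. The next paragraph gives an average of four data collections out of four possible. Section 5.9.4 plans a GEE analysis for repeated measures.

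**The concern.** Four reports from one person with an intra-class correlation of 0.3-0.4 carry much less information than four independent reports, and the sample size should show it. Table 4 barely does. Full independence would need 501 people per arm for 11% vs 8%. The table asks for 522 at 0.3, about 4% more. Moving from 0.3 to 0.4 adds about 3% (522 to 537), where a true ICC would add about 16% (951 to 1,101).

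At stake is the stated power for the primary endpoint of this component. The GEE analysis will estimate its standard errors with the actual within-person correlation. If that correlation is what the protocol says, the shortfall will appear as wider intervals and a higher chance of missing the assumed effect.

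**Working it through.** **Inputs (all from Section 5.9.2 and Table 4).** Two-sided alpha 5% and power 90%, so (1.960 + 1.2816)² = 10.507. Rates p0 = 0.11 and p1 = 0.08, so d = 0.03. Visits m = 4 in Table 4, or 3.75 among retained participants. ICC 0.3-0.4. Per arm: 522 (or 537) stated, 660 enrolled, 0.90 × 660 = 594 with follow-up.

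**Step 1: reproduce the plan's figures.** Section 5.9.2 does not name its formula. Sections 3.8.2 and 4.8.2 cite a between-cluster-variability method for the site-randomised components. Treating each person as a cluster of m visits, that type of formula is

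n = 1 + 10.507 × [(p0q0 + p1q1)/m + k²(p0² + p1²)] / d²

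where k is the coefficient of variation of person-level rates. Here p0q0 + p1q1 = 0.0979 + 0.0736 = 0.1715, and p0² + p1² = 0.0185.

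- k = 0.3: 1 + 10.507 × (0.042875 + 0.001665)/0.0009 = 521.0 (just above 521), rounded up to 522. Stated: 522.
- k = 0.4: 1 + 10.507 × (0.042875 + 0.002960)/0.0009 = 536.1, rounded up to 537. Stated: 537.

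The same formula, rounded up, returns all 18 cells of Table 4 exactly. Entering 0.3 or 0.4 as an ICC through the usual design effect returns none of them.

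**Step 2: the ICC that k implies.** The between-person variance is k²p² and the total variance is p(1−p), so ICC = k²p/(1−p).

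| Rate | k = 0.3 | k = 0.4 |
|---|---|---|
| 11% | 0.011 | 0.020 |
| 8% | 0.008 | 0.014 |

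**Step 3: required size if 0.3-0.4 is an ICC.** n = 10.507 × 0.1715 × [1 + (m−1)ICC]/m / d², with m = 4.

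- ICC 0.3: design effect 1.9; n = 10.507 × 0.1715 × 1.9/4/0.0009 ≈ 951 per arm.
- ICC 0.4: design effect 2.2; n ≈ 1,101 per arm.

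Pooled-variance versions give 953 and 1,103. Over the whole table, the ICC-based requirement is about 1.8 to 2.1 times the printed figure.

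**Step 4: power if 0.3-0.4 is an ICC.** Power = Φ{ d / √(0.1715 × [1 + (m−1)ICC]/(m·n)) − 1.96 }.

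- 522 per arm, m = 4, ICC 0.3: standard error √(0.1715 × 1.9/2,088) = 0.01249; 0.03/0.01249 = 2.40; power 67%.
- 522 per arm, m = 4, ICC 0.4: standard error 0.01344; ratio 2.23; power 61%.

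| Assessed per arm | Visits | ICC 0.3 | ICC 0.4 |
|---|---|---|---|
| 522 | 4 | 67% | 61% |
| 594 | 3.75 | 72% | 66% |
| 660 (no loss) | 4 | 77% | 71% |

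**Step 5: detectable effect.** With 594 per arm and 3.75 visits, 90% power is reached at 11% vs 7.2% (ICC 0.3) or 11% vs 7.0% (ICC 0.4).

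**The case against.** **The cause is inferred, and a mislabel would rescue the power.** The protocol names no formula for Table 4. If the values taken from the SMART data were coefficients of variation, only the label is wrong and 90% stands. This limit is real, because those data are not in the protocol. A reader might infer that the trial simply lacks the power it claims; the document supports that only if 0.3-0.4 is an ICC. But both the text and the table headings call it an ICC, and the mislabel reading needs repeated reports of sexual behaviour by one person to be almost uncorrelated, which nothing in the protocol supports. On either reading the section is inconsistent.

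**The lower power range is not the planned design.** The 61-67% belongs to 522 assessed. The enrolment and retention figures give 594 at 3.75 visits, hence 66-72%. It is tempting to say that the assumed effect would be missed one time in three or more. For the planned design the miss rate is about 28% at ICC 0.3 and 34% at ICC 0.4, so that statement fails at the lower ICC.

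**The surrounding figures look worse than they are.** 594 against 522 is not a clear contradiction: 594 × 3.75 ≈ 2,228 visits exceeds 522 × 4 = 2,088, so it can be read as a margin. The 3.75 and 4 visits do disagree, but power moves by only about one percentage point (67% to 66% at 522, ICC 0.3). Section 5.9.2 says "It is estimated that around 110 participants will be recruited per HIV care site", while Section 6.5 says "Up to 110 individuals will be assigned to each arm, per site". A reader might infer 12 × 2 × 110 = 2,640 participants. The words in Section 6.5 set a ceiling, however, and accrual stops at 1,320, so that total cannot arise.

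**Scope.** The error concerns the stated power of one component. It does not bias the estimate or alter the type I error.

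**Conclusion.** The point holds in conditional form. Table 4 and the stated ICC cannot both be right. All 18 entries follow from using 0.3 or 0.4 as a coefficient of variation, equivalent to an ICC of about 0.01-0.02 at 8-11%. Taking the protocol at its word, 11% vs 8% at 90% power needs about 951-1,101 assessed per arm. Power is about 61-67% at 522 per arm and 66-72% for the planned design. Even complete follow-up of all 660 per arm reaches only 71-77%, so no reading of the retention or visit figures restores 90%.

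This rests on an exchangeable within-person correlation, equal numbers of visits per person and a normal approximation. The use of the coefficient-of-variation formula is a strong inference, not something the protocol states. The loss of power does not depend on that inference, only on the ICC being 0.3-0.4. The differences in assessed numbers, visits and per-site figures are wording to align, not part of the main error.

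**What to change.** Check what the SMART values were, then take one of two routes.

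- **If they are ICCs:** recompute Table 4 with the design effect 1 + (m−1)ICC. Then either state the power for 1,320 enrolled (594 per arm with follow-up, 3.75 visits) as about 66-72% for 11% vs 8%, or state the effect detectable at 90% power as 11% vs about 7.0-7.2%.
- **If they are coefficients of variation:** relabel them in the text and table, give the implied ICC of about 0.01-0.02, and justify it.

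In both cases use one set of figures for assessed participants (522 or 594), mean visits (3.75 or 4) and per-site numbers. With 1,320 over 12 sites, Section 6.5 would read about 55 per arm per site.

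Optionally, adjust the analysis for the month-0 report, which is already collected. Under exchangeable correlation the variance is multiplied by 1 − ICC²/{[1 + (m−1)ICC]/m}. At 3.75 visits this is 1 − 0.09/0.487 = 0.815 (ICC 0.3) or 1 − 0.16/0.56 = 0.714 (ICC 0.4), giving about 80% power at 594 per arm. This does not restore 90% and is not needed to correct the error.

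The cost is one table and a few sentences. On the ICC route the stated power falls. No added enrolment is required to make the document correct.
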